We are currently testing the efficacy of a tailored DVD mailed to a woman's home against an interactive tailored phone intervention for women aged 50 to 75 who are nonadherent to BC screening. Preliminary data from the study indicated that there was a significant difference (p<0.05) in mammography adherence at 1 month between women receiving a DVD (18%) or a phone counseling session (20%) as compared to usual care (10%). At six months, the adherence levels were 61% for the DVD group, 56% for the phone counseling group, and 45% for the usual care group. Additionally, we found that 83% of women who received a mailed DVD completed the interactive DVD and reported it to be highly usable (Mean of 4.79 on a 5 point scale). Although data are preliminary, it can be concluded that women used the DVD when mailed to their homes and that both the mailed DVD and phone counseling session were significantly more effective than usual care.

Finally, Drs. [name], [name], and [name] are testing a tailored interactive computer program designed to promote CRC screening among African Americans in a primary care setting through a current intervention trial funded by the National Cancer Institute (1R01 CA115983, 2006-2011). Prior to this trial, Drs. [name], [name], and [name], with support from the Walther Cancer Institute, collaborated on the development of an interactive computer intervention designed to increase CRC screening among African Americans. Variables that are being assessed and used to generate tailored messages include health beliefs such as perceived risk of CRC, perceived benefits and perceived barriers to screening, self-efficacy, and stage of adoption. Preliminary results from this ongoing pilot study showed that, among persons who were noncompliant with FOBT at baseline, participation increased to 43% in the interactive computer group compared to no change in the control group. Satisfaction with the program was very high; of 36 African Americans who evaluated the program, 100% indicated they found the program interesting, easy to use, easy to understand, and that it provided important information.

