In Table 8 of the original application (see appendix), we proposed enrolling 327 for each of 8 combinations of 4 arms and 2 groups (A and B) for a study total of 2616. However, using this alternative approach will require only 1308 (327 in each of the 4 arms) women to test the primary outcome of CRC adherence. However, new studies, including our own, indicate 15-20% adherence to CRC screening in control conditions. Our initial proposal anticipated on 10% adherence in the control arm. Thus, although the new design decreases the sample size by combining the groups, a more realistic estimate of the adherence in the control group will actually increase the sample size compared to our estimate in Group A for the initial proposal. Specifically, we propose to increase our estimate of CRC adherence in all four arms, to accommodate a change in the proposed adherence in the control group from 10% to 20%. This will require 397 instead of 327 per arm (see Table 1). Thus, a sample of 397 per group at baseline (357 per group at 6 months after 10% estimated attrition) will provide 80% power to detect differences between any pair of the four randomized arms for Aim 1 (Table 1).

Revised Sample size and Power analysis for primary efficacy hypothesis of estimated CRC screening adherence rates in the combined groups of those adherent (Group A) and non-adherent (Group B) at baseline to breast cancer screening (Aim 1, primary outcome of CRC adherence)

GROUPS A and B combined

Time	Usual Care (1)	TIDVD (2)	CSC (3)	TIDVD+CSC (4)	Power
Baseline adherence	0%	0%	0%	0%	NA
Total sample size (N):	(n = 397)	(n = 397)	(n = 397)	(n = 397)	
N by baseline strata, Adherent to BC (A) Non-adherent to BC (B)	(n = 119) (n = 278)				
6 months adherence	20%	30%	40%	55%	Power for 357/arm (Groups A and B combined)
Total sample size (N):	(n = 357)	(n = 357)	(n = 357)	(n = 357)	1v2 .87 1v3 .99 1v4 .99 2v3 .80 2v4 .99 3v4 .98
N by baseline strata, Adherent to BC (A) Non-adherent to BC (B)	(n = 107) (n = 250)				

Enrollment will be stratified by women adherent to breast but not CRC screening and those adherent to neither in a 30%/70% ratio so that we will have an adequate sample to detect an 80% power for Aim 2. Aim 2 will use only the subgroup of women who are not adherent to either breast or CRC screening. This will provide at least 80% power for Group B for comparing each pair of randomized arms, when testing the secondary outcome (adherence to both CRC and BC screening) (Table 2).

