Program Effectiveness: The main effect is screening compliance at 6 months from the baseline measure as determined by the randomized trial. For those in **Group A**, CRC screening is the outcome. For **Group B**, there are three outcome groups: CRC screening adherence, BC screening adherence, and adherence to CRC and BC screening. Outcomes will be determined with an “intent-to-treat” analysis by analyzing data from all women who originally consented and were randomly assigned to a research arm regardless of deviations from the protocol, the degree of treatment they received (e.g., regardless of whether TIWeb was viewed or CSC was made), or withdrawal from treatment or loss to follow-up. The use of claims data and medical records data for the main outcome of adherence will make it possible to analyze adherence at 6 months even for women who dropped out, as long as claims data for those women can be obtained.

Program Costs: To calculate the costs of the interventions, we will consider delivery costs only. Costs associated with research and development (R&D) activity or costs of screening tests are excluded. The cost of developing the TIWeb is expected to be a major pre-intervention R&D cost. Researchers have debated how to handle these “first-copy” costs and there is no universally accepted “correct” answer. First-copy costs, defined as costs incurred in establishing a regimen or intervention, are considered quasi-fixed costs independent of the number of units produced, once production is started. Generally, first-copy costs are excluded when they involve situations in which much of the intervention is already in existence and only modification is needed to adapt it for implementation. While R&D costs can be high, they are “sunk cost” from a societal perspective, in any future decision to implement the interventions. The final product developed for this study could be made available to

other organizations. We expect managed care organizations would not develop their own TIWeb, but would rely on public access or licensing arrangements to secure such educational material. However, the cost of developing the TIWeb will be calculated to inform future developers of the approximate cost of developing this type of interactive technology for health promotion interventions and to test CE analysis with and without these costs.

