The primary cost-effectiveness measures will be the incremental cost-effectiveness ratios (ICERs) obtained by dividing the additional per target individual cost by the additional percent of target individuals who are screened by the end of the follow-up period, comparing the control group to the TIWeb group, to the CSC group, to the TIWeb+CSC group moving from the least resource-intensive to the most resource-intensive interventions (equations 1,2,3). These measures will be based on intention to treat methods and correspond to the observation period of the study.⁽¹⁴⁵⁾

Group A (cost fully allocated to BCS intervention)

- 1) $ICER_1 = (Cost_{TIWeb} - Cost_{UC}) \div (\%BCS_{TIWeb} - \%BCS_{UC})$
- 2) $ICER_2 = (Cost_{CSC} - Cost_{TIWeb}) \div (\%BCS_{CSC} - \%BCS_{TIWeb})$
- 3) $ICER_3 = (Cost_{TIWeb+CSC} - Cost_{CSC}) \div (\%BCS_{TIWeb+CSC} - \%BCS_{CSC})$

Group B (cost adjusted for joint production)

BCS: (directly allocated plus 1/2 of non directly allocated cost applied to BCS intervention)

- 1) $ICER_1 = (Cost_{TIWeb} - Cost_{UC}) \div (\%BCS_{TIWeb} - \%BCS_{UC})$
- 2) $ICER_2 = (Cost_{CSC} - Cost_{TIWeb}) \div (\%BCS_{CSC} - \%BCS_{TIWeb})$
- 3) $ICER_3 = (Cost_{TIWeb+CSC} - Cost_{CSC}) \div (\%BCS_{TIWeb+CSC} - \%BCS_{CSC})$

CRC: (directly allocated plus 1/2 of non directly allocated cost assigned to CRCS intervention)

- 1) $ICER_1 = (Cost_{TIWeb} - Cost_{UC}) \div (\%CRCS_{TIWeb} - \%CRCS_{UC})$
- 2) $ICER_2 = (Cost_{CSC} - Cost_{TIWeb}) \div (\%CRCS_{CSC} - \%CRCS_{TIWeb})$
- 3) $ICER_3 = (Cost_{TIWeb+CSC} - Cost_{CSC}) \div (\%CRCS_{TIWeb+CSC} - \%CRCS_{CSC})$

BCS & CRCS: (all costs allocated to joint BCS & CRCS intervention)

- 1) $ICER_1 = (Cost_{TIWeb} - Cost_{UC}) \div (\%BCS \& CRCS_{TIWeb} - \%BCS \& CRCS_{UC})$
- 2) $ICER_2 = (Cost_{CSC} - Cost_{TIWeb}) \div (\%BCS \& CRCS_{CSC} - \%BCS \& CRCS_{TIWeb})$
- 3) $ICER_3 = (Cost_{TIWeb+CSC} - Cost_{CSC}) \div (\%BCS \& CRCS_{TIWeb+CSC} - \%BCS \& CRCS_{CSC})$

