The effects on the ICERs of methods and parameter uncertainty will be assessed by one-way and/or multi-way sensitivity analysis. For example, ICERs may be sensitive to wage rates of key personnel and the overhead rates. Statistical uncertainty in the cost-effectiveness ratios will be assessed with 1,000 bootstrap samples. The outcome of each bootstrap sample will be expressed as a point on a scatter plot of incremental costs and percent screened and reflects the uncertainty arising from the model parameters. Scatter plots of the incremental costs and effects will be used to define the 95% confidence limits around the cost-effectiveness ratios.⁽¹⁴⁶⁾

Aim 3: Interaction analysis.

Hypothesis 1 Interactions: We will use interaction terms in the logistic regression models, developed above for analyses of Aim 1, to test whether intervention effects depend on knowledge, cancer screening beliefs, health status, demographic variables (age, race, education, and marital status), screening history, out-of-pocket costs for screening, baseline stage of adoption, provider recommendation, and participant involvement in the intervention. We will also test the interaction between each intervention and whether participants sought help through additional contact(s) with the research assistants. If an interaction is significant, we will use parameter estimates from the logistic regression model to estimate odds ratios for intervention effects at various levels or scores of the interacting covariates (e.g., within each race or site, or at various values, for example quartiles, of perceived barriers). Because many interactions will be tested, we will adjust for multiple comparisons (see below).

Hypothesis 2 Site Differences: We will compare screening adherence between the group of women who receive care in sites that have colonoscopy available with those who are not in such sites using logistic regression after adjusting for randomized group (usual care, TIWeb, CSC, and TIWeb + CSC).

Adjustment for multiple comparisons: Because many tests will be performed in Exploratory Aim 3, we will report p-values adjusted for multiple comparisons in the analyses, using the resampling step-down adjustment method of Westfall and Young,⁽¹⁴⁷⁾ which accounts for the dependence structure between related tests.

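### The Aim 2 cost-effectiveness ratios use a fixed arm order with no rule for dominated arms or for effect differences near or below zero, which matters most in Group A

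*Combined protocol and SAP*

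**What the plan says.** The Aim 2 part of section D.13 makes incremental cost-effectiveness ratios (ICERs) the primary measures. Each comes from "dividing the additional per target individual cost by the additional percent of target individuals who are screened by the end of the follow-up period", with neighbouring arms compared "moving from the least resource-intensive to the most resource-intensive interventions". The printed formulas fix that order:

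- ICER1 is TIWeb against usual care.
- ICER2 is CSC against TIWeb.
- ICER3 is TIWeb+CSC against CSC.

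There are three such ratios for Group A. Group B has nine: three each for BC screening, CRC screening and both.

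On uncertainty, the same section says "Statistical uncertainty in the cost-effectiveness ratios will be assessed with 1,000 bootstrap samples". Each sample is plotted as a point of incremental cost against percent screened, and "Scatter plots of the incremental costs and effects will be used to define the 95% confidence limits around the cost-effectiveness ratios". The plan does not say how the limits are read from the plot. It also does not say what happens to points with an effect difference at or below zero, or to an arm that costs more and screens fewer women. One-way or multi-way sensitivity analysis is planned, with wage and overhead rates as examples.

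The Group A formulas are headed "Group A (cost fully allocated to BCS intervention" and use the percentage with BC screening. Under Program Effectiveness, the text says that for Group A "CRC screening is the outcome".

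**The concern.** A ratio is well behaved only when its denominator is clearly away from zero. If the 95% interval for the difference in percent screened includes zero, the 95% confidence set for the ratio (Fieller's construction) is unbounded. A negative ratio is also ambiguous: it can mean an arm that is cheaper and better, or one that is dearer and worse.

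The ICERs are formed within Groups A and B, so the power quoted in section D.12 for the two groups combined does not apply to them.

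The fixed chain adds a second problem. If CSC costs more than TIWeb and screens no more women, CSC is dominated and should leave the comparison. As written, ICER3 would still use it as the comparator. Aim 2 is one of the specific aims, and its headline results could be hard to interpret in Group A and misleading for the combined arm.

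**Working it through.** **Inputs.** From the D.12 table: 6-month CRC adherence of 20%, 30%, 40% and 55%; 357 per arm in total at 6 months, split into 107 (Group A) and 250 (Group B); 119 per arm in Group A at baseline. Alpha is not stated, so two-sided 0.05 is assumed. The rates are given only for the groups combined; applying them within each group is an assumption.

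**Formula.** With p̄ the mean of the two rates,

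power = Φ{ [d − 1.96·√(2p̄(1−p̄)/n)] / √[(p₁(1−p₁)+p₂(1−p₂))/n] }.

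**The plan's own figure.** For 20% v 30% at n = 357: 1.96·√(0.375/357) = 0.0635; SE = √(0.37/357) = 0.0322; (0.10 − 0.0635)/0.0322 = 1.13; Φ = 0.87. This matches the table, as do the other two neighbouring pairs.

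**At the sizes the ICERs use.** For 20% v 30% at n = 107: 1.96·√(0.375/107) = 0.1160; SE = √(0.37/107) = 0.0588; (0.10 − 0.1160)/0.0588 = −0.27; Φ = 0.39. In full:

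| Denominator | Rates | Combined, 357 (plan) | A, 107 | A, 119 | B (CRC), 250 |
|---|---|---|---|---|---|
| ICER1 | 20 v 30 | 0.871 (.87) | 0.39 | 0.43 | 0.73 |
| ICER2 | 30 v 40 | 0.801 (.80) | 0.33 | 0.37 | 0.65 |
| ICER3 | 40 v 55 | 0.981 (.98) | 0.60 | 0.64 | 0.92 |

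If the observed differences equal the planned ones, the 95% intervals for the denominators (d ± 1.96·SE, in points) are:

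- Group A: −1.5 to 21.5, −2.7 to 22.7, and 1.8 to 28.2.
- Group B: 2.5 to 17.5, 1.7 to 18.3, and 6.3 to 23.7.

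**What the scatter would show.** In the same case, the share of bootstrap points at or below zero effect is Φ(−d/SE). For Group A this is 4.5%, 6.2% and 1.3%; for Group B it is 0.5%, 0.9% and 0.03%. A simulation of 4,000 trials with 1,000 bootstrap samples each counted trials with at least 2.5% of points at or below zero. It gave 62%, 69% and 43% in Group A, and 27%, 36% and 9% in Group B.

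If limits were taken as percentiles of the ratio and the added cost were positive, the points with a negative effect would sort to the low, favourable end. In Group A, 4.5% and 6.2% exceed the 2.5% tail. The lower limits of ICER1 and ICER2 would then come from samples in which the dearer arm did worse.

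**Dominance.** Section C reports 6-month mammography adherence of "61% for the DVD group, 56% for the phone counseling group", a phone-minus-DVD difference of −5 points. The four-arm trial there reports, at two months, 38% for the letter, 36% for telephone and 40% for both, a telephone-minus-letter difference of −2 points. If such rates recurred, the chance that the observed ICER2 denominator is at or below zero is:

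- 61% v 56%: Φ(0.05/0.0673) = 0.77 at 107 per arm, and 0.87 at 250.
- 38% v 36%: 0.62 at 107 per arm, and 0.68 at 250.

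In 99–100% of simulated trials the ICER2 denominator would be negative or its interval would include zero.

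ICER3 is then distorted too. With 38%, 36% and 40%, the chain's denominator is 40 − 36 = 4 points. With the dominated arm removed it is 40 − 38 = 2 points. If CSC costs more than TIWeb, the chain's numerator is also too small. Both errors make the combination look better value than it is.

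**The case against.** A reader might infer that the limits will be meaningless throughout because they are percentiles of an unstable ratio. The documents do not support that. D.13 plots cost and effect jointly, which keeps the sign of each and is a sound display. It does not say that the limits are percentiles of the ratio, and it cites a methods source that may settle the matter. In Group B, the CRC denominators are more likely than not to be distinguishable from zero, and the third Group A step has power 0.60. This part of the objection stands: the problem is an unspecified construction that is fragile mainly in Group A.

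The earlier trials are also weak evidence on dominance. They concern mammography, and they tested a DVD and a letter rather than a website. The planned rates put CSC above TIWeb. So the documents do not show that CSC will be dominated, only that it is plausible enough to need a rule.

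Intention-to-treat analysis with claims data for dropouts could bring the Group A size nearer 119. That changes little, as the table shows.

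Finally, net benefit needs a value per additional woman screened, which the documents do not give, and it does not cure small numbers. Both points are true. But net benefit is linear in the effect difference, so it keeps its meaning at or below zero, where a ratio does not. And the fixed chain goes beyond missing detail: its third formula names CSC as comparator whatever the results.

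**Conclusion.** The point holds for Group A and for the fixed chain. At the planned CRC rates, the ICER1 and ICER2 denominators in Group A are more likely than not to be compatible with zero (chances 0.61 and 0.67, from 1 − 0.39 and 1 − 0.33). The third has a chance of about 0.4. Finite, interpretable limits are therefore unlikely for two of the three Group A ratios, while most Group B CRC ratios would be usable.

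This assumes two-sided 0.05, the combined rates in each group, and CRC screening as the Group A outcome. Nothing can be said about six of the nine Group B ratios, because rates for BC and joint screening are not in the text. D.12 claims at least 80% power for Group B on the secondary outcome, but the table behind that claim is not shown.

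Separately, if the call does no better than TIWeb, ICER2 has a zero or negative denominator. If the call also costs more, ICER3 uses a dominated comparator.

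**What to change.** 1. Within each group and each perspective, order the arms by observed cost. Remove dominated and extendedly dominated arms before forming ICERs. The order may differ by perspective, since participant time is excluded from the provider's costs.
2. Keep the 1,000 bootstrap samples and the scatter plots. From them report incremental net benefit, λ·ΔE − ΔC, with 95% intervals over a stated range of λ (the value per additional woman screened), and acceptability curves for the four arms.
3. State how ratio limits are derived, and give them only where the interval for the effect difference excludes zero. Elsewhere report the differences in cost and effect and the net benefit.
4. Reconcile the Group A outcome: BC screening in the ICER formulas, CRC screening under Program Effectiveness.

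The cost is some extra analysis of the same data and samples. A value range must be chosen, preferably before results are seen, and the Group A intervals will still be wide.

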¹²⁸⁾ and consistent with our previous research.^(9, 10) Construct validation for these stage measures was established via principal components analyses in an original and a replication study (involving 142 and 676 women, respectively).^(119, 128) Items for CRC and BC screening will determine whether participants: 1) have ever had a mammogram, FOBT, sigmoidoscopy, or colonoscopy; 2) have thought about having a mammogram, FOBT, sigmoidoscopy, or colonoscopy; or 3) intend to have any of these tests in the next six months. We will also ask participants if CRC or BC screening tests were for screening or diagnostic purposes and use their responses as a covariate. Screening and diagnostic procedures have different CPT codes.

Mammography and colonoscopy scheduling will be based on the location of the participating physician. The study team will be given a preferred list of sites to be scheduled as well as alternative sites if the patient chooses. Results of screenings will be sent immediately to the participant's primary health care provider as part of her routine care.

Past Screening History will be measured by self-reported items that assess CRC and BC screening tests women have had in the past 20 years or since the individual turned 50. Self-report will be the most feasible method to assess screening history since claims data may not accurately reflect all screening tests done in other health care settings or while they were covered by a different health insurance plan.

Participant Involvement: will be measured for the TIWeb and for the CSC. The participant involvement scale for TIWeb has 19 items that address interest and engagement in the program and its content. The items, piloted with 36 people (see Preliminary Studies), address ease of use, relevancy, information content, barriers, and general satisfaction. The Cronbach's alpha was 0.89 and 100% of people indicated that they found the program interesting, easy to use, easy to understand, and containing information that was important to them. The survey instrument can be found in **Appendix E**. There are 15 items that measure participant involvement in the CSC. Participants will be called within 4 weeks following intervention to obtain data on involvement with the intervention.

Beliefs about CRC or BC Screening

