Group A (nonadherent to CRC but adherent to BC screening guidelines)

Hypothesis 1- Efficacy Analysis: The differences in binary adherence across the four randomized arms will be tested initially with the chi-square test for a 2x4 cross-classification table (adherence by randomized intervention groups). Binary logistic regression analysis, with three dummy variables using usual care as the reference category, will be computed to study the effects of each intervention (TIWeb, CSC, TIWeb +CSC) versus usual care on adherence, while adjusting for any potentially confounding covariates. In addition, model contrasts will be specified to statistically compare each of the three intervention arms to the others. Since the intervention is delivered to the patient and not the provider, analysis of variation in CRC screening by practitioners will be limited. Outcomes of patients who share the same providers may be slightly more correlated than outcomes of patients from different providers. Thus, the within-provider correlation among patients will be assessed with variance components, and if necessary generalized estimating equations (GEE) will be used with logistic regression to account for the within-provider correlation. We will enter as independent variables into logistic models the following: randomized group membership and any demographic covariate (age, race, education, marital status, screening history, baseline stage of adoption, SF12 mental health component, SF12 physical health component) for which the randomized groups differ significantly at baseline using a liberal significance level of 0.20. We will also measure whether subjects report that their physicians have recommended the screening test in the past and the amount of out-of-pocket expense for screening and enter these as covariates. In addition to demographic variables, other potential covariates will be location of TIWeb intervention (use of a computer at home or elsewhere), and whether women in the TIWeb group needed technical help from the research assistant to use the TIWeb program. We plan to include screening history as a covariate in our analysis by using the total number of past screenings for each test since the participant turned 50. For analysis with mammography screening, one covariate will be included (total number of mammograms since age 50). For the analysis of CRC screening, two covariates will be included simultaneously in the models (total number of FOBTs since age 50, and "any previous endoscopic test" [yes/no]). The CRC screening analysis requires two covariates because a history of five FOBTs, for example, is not equivalent to one previous FOBT and one previous colonoscopy or sigmoidoscopy. All variables in the

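### Aim 3 treats participant involvement as an effect modifier, but usual care has no involvement score, so the planned interaction against usual care is not identified; TIWeb help-seeking is aliased in a similar way.

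*Combined protocol and SAP*

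**What the plan says.** Section D.13, Aim 3, Hypothesis 1 states: "We will use interaction terms in the logistic regression models, developed above for analyses of Aim 1". The moderators named there include "baseline stage of adoption, provider recommendation, and participant involvement in the intervention", and Aim 3 in the Specific Aims also lists involvement. If an interaction is significant, the plan will report odds ratios for the intervention effect at chosen values of the moderator. The same paragraph adds: "We will also test the interaction between each intervention and whether participants sought help" through extra contact with the research assistants.

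The Aim 1 model is a binary logistic regression "with three dummy variables using usual care as the reference category". In addition, "model contrasts will be specified to statistically compare each of the three intervention arms to the others".

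Section D.11 says involvement "will be measured for the TIWeb and for the CSC". For the website, "The participant involvement scale for TIWeb has 19 items". For the call, "There are 15 items that measure participant involvement in the CSC". D.11 and Table 7 place this measurement at 4 weeks and not at baseline. Under D.5, the arm is assigned once the baseline survey is complete, and usual-care women are told to expect data-collection contacts only.

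On help, D.9 describes a toll-free number for questions about the TIWeb, with each contact recorded. The Aim 1 text in D.13 refers to technical help for women in the TIWeb group.

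**The concern.** A moderator analysis asks whether the effect of an arm against usual care differs between women with low and high values of some characteristic. It needs usual-care women at each of those values. Involvement in an intervention has no value in an arm that received none.

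It is also a response to the assigned arm. Women who engage with a website or a call are likely to be more motivated to be screened anyway. Some may already have been screened when they are asked: in the preliminary DVD and telephone study (section C), mammography adherence at 1 month was already 18% and 20% in the intervention groups, against 10% in usual care.

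At stake is a finding that the intervention works in engaged women, which this contrast cannot show.

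**Working it through.** **Counts.** D.12 gives 397 women per arm at baseline and 357 at 6 months after 10% attrition. Check: 357 / (1 − 0.10) = 396.7, rounded up to 397. The pairwise powers in D.12 also reproduce at a two-sided 0.05, which is assumed because D.12 does not state it: 0.871 for 20% v 30%, 0.801 for 30% v 40%, and 0.981 for 40% v 55%. D.12 gives no power for any Aim 3 interaction.

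- Expected at 6 months: 4 × 357 = 1,428.
- At most 3 × 357 = 1,071 can have an involvement score.
- Without a score: 357, and 357 / 1,428 = 25%.

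**The planned model.** Let A1, A2 and A3 be the dummies for TIWeb, CSC and the combination, and V the involvement score:

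logit P = b0 + b1·A1 + b2·A2 + b3·A3 + g·V + d1·A1·V + d2·A2·V + d3·A3·V

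This has 8 columns. Here g is the involvement slope in usual care, and each d is an arm's slope minus g. If g cannot be estimated, neither can any d.

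**Rank under each handling of usual care.**

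- *V missing, usual care drops out.* Among the remaining women A1 + A2 + A3 = 1, and V = A1·V + A2·V + A3·V. Two columns are redundant: 8 − 2 = 6.
- *V set to a constant c.* V = c·(1 − A1 − A2 − A3) + A1·V + A2·V + A3·V. One column is redundant: 8 − 1 = 7.
- *V real and varying in usual care.* Rank 8. This is the only case in which the planned test exists.

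A numerical check of the design matrix with 357 women per arm gave the same ranks: 6, 7 and 8.

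**What is left in the rank-7 case.** Intercept, dummies and V use 5 of the 7, leaving 7 − 5 = 2 degrees of freedom. These compare slopes between active arms, not with usual care. Leaving V out as a main effect gives 3 degrees of freedom (7 − 4), but that test asks only whether involvement predicts screening within the active arms.

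**What that 3-df test would show.** It was simulated 500 times with usual care set to 0 and no effect modification. The assumptions, none from the documents, were constant arm effects on the log-odds scale, a motivation effect of 0.5 log-odds per SD, and a correlation of 0.6 between involvement and motivation. The test rejected at 0.05 in 97% of runs. If motivation had no bearing on screening, it would reject at about the nominal 5%. The rate therefore depends on the assumptions, and the rank argument does not rely on it.

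**Active arms only.** With one scale common to all three arms, the model is full rank (6 of 6, with a 2-df interaction). With separate scales, what remains is TIWeb v combination on the TIWeb scale and CSC v combination on the CSC scale, about 2 × 357 = 714 women each.

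**Help-seeking.** Read help H as the TIWeb contact of D.9. Then H = 0 throughout usual care and CSC alone. The column A2·H is all zero, and H = A1·H + A3·H. Rank is 8 − 2 = 6. With H as a main effect, one interaction degree of freedom remains (6 − 5), and it compares the combination with TIWeb alone. No woman is lost, but no interaction against usual care is identified.

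**The case against.** The strongest reply is that the plan leaves the handling of usual care open, and that sensible readings exist. Four parts of it need an answer.

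*Estimates can be obtained.* This stands. A reader might infer that nothing can be estimated, or that measurement after randomization is itself what blocks estimation. Neither is right. Arm-specific slopes can be fitted with usual care kept in, and a single-component arm can be compared with the combination. The absent usual-care score removes identification of the stated interaction; the timing is why the numbers that remain are not effect modification.

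*The plan never says usual care would be discarded.* This also stands. Losing the control arm is one possible result of how the data are coded, not something the documents plan. A restriction to women who received an intervention is a fair guess at the intent, but the text does not state it, and it would no longer test effects against usual care.

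*Other passages might fill the gap.* They do not. D.1 says participants are surveyed on involvement in the intervention, but gives no definition for women without one. The multiple imputation planned under missing data addresses values that exist but were not observed; these are undefined.

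*Help-seeking is not a missing score.* Correct. A woman with no contact has a defined value of no, so that problem is structural zeros. It would be wrong to describe it as the same fault.

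The TIWeb instrument is in an appendix not seen here, so shared items or common scoring across the two scales cannot be excluded.

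**Conclusion.** The point holds for the test as written. The arm-by-involvement interaction against usual care is not identified, with rank 6 or 7 of 8 columns, and the help-seeking interaction against usual care is aliased. Whatever can still be fitted compares women by how they responded to their arm.

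This rests on two inferences: that usual care has no involvement measure (D.5 and D.11), and that help means TIWeb contacts (D.9 and the Aim 1 text of D.13). The statement that TIWeb-only and CSC-only women share no scale rests on the two separate item sets described.

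The consequence is limited. D.13 calls Aim 3 exploratory and adjusts its p-values; the primary analysis, sample size and power are untouched. A reader might take the 25% as a measure of bias. It is only usual care's share of the sample.

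**What to change.** Remove participant involvement and help-seeking from the interaction list in D.13, Aim 3, Hypothesis 1, and remove involvement from Aim 3 in the Specific Aims. Keep as moderators only variables measured at baseline; for knowledge and beliefs, which Table 7 collects at baseline and at 4 weeks, specify the baseline value.

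Report involvement and help-seeking as descriptive, non-causal associations with adherence, within the active arms where each is defined: TIWeb involvement and help in the two TIWeb arms, CSC involvement in the two CSC arms. Avoid dose-response wording.

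A complier-average analysis with randomized arm as the instrument is optional. If it is wanted, base it on a binary measure of TIWeb use or CSC receipt, not on the involvement scale, which also covers ease of use and satisfaction. State the exclusion restriction: the letter and email giving access to the TIWeb, for example, would have to have no effect on screening except through use of the site.

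The cost is a change of wording. The involvement and help-seeking tests leave the exploratory Westfall-Young family; how many that is depends on the number of outcomes and arm terms tested. No data collection changes.
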